### **9.5.3 Dosing Errors**

Study Drug (ISIS 681257 or placebo) errors should be documented as Protocol Deviations. A brief description should be provided in the deviation, including whether the patient was symptomatic (list symptoms) or asymptomatic, and the event was accidental or intentional.

Dosing details should be captured on the Dosing Case Report Form. If the patient takes a dose of Study Drug (ISIS 681257 or placebo) that exceeds protocol specifications and the patient is symptomatic, then the symptom(s) should be documented as an AE and be reported per [Section 9.4](#).

**Should an overdose occur**, the Investigator or designee should contact the Sponsor or designee within 24 hours.

#### **9.5.4 Contraception and Pregnancy**

Male and female patients of childbearing potential must continue to use appropriate contraception with their partners, or refrain from sexual activity, as described in [Section 6.3.1](#).

If a patient becomes pregnant or a pregnancy is suspected, or if a male patient makes or believes that he has made someone pregnant during the study, then the Study Center staff must be informed immediately. An Initial Pregnancy Form should be submitted to the Sponsor or designee **within 24 hours** of first learning of the occurrence of pregnancy. Follow-up information including delivery or termination is reported by designating as ‘Follow-up’ on the Pregnancy Forms and reported within 24 hours of occurrence.

Payment for all aspects of obstetrical care, child or related care will be the patient’s responsibility.

Female patients: If a suspected pregnancy occurs while on the study (including during the follow-up period), a pregnancy test will be performed. The patient with a confirmed pregnancy will be immediately withdrawn from treatment with Study Drug. However, the patient will be encouraged to complete the Post-treatment Follow-up portion of the study to the extent that study procedures do not interfere with the pregnancy. Regardless of continued study participation, the Investigator will assist the patient in getting obstetrical care and the progress of the pregnancy will be followed until the outcome of the pregnancy is known (i.e., delivery, elective termination, or spontaneous abortion). If the pregnancy results in the birth of a child, the Study Center and Sponsor may require access to the mother and infant’s medical records for an additional 8 weeks after birth. Follow-up will be performed to the extent permitted by the applicable regulations and privacy considerations.

Male patients: The progress of the pregnancy of a male patient’s partner should be followed until the outcome of the pregnancy is known (i.e., delivery, elective termination, or spontaneous abortion). If the pregnancy results in the birth of a child, **the Study Center and Sponsor may request access to the mother and infant’s medical records for an additional 8 weeks after birth.** Follow-up will be performed to the extent permitted by the applicable regulations and privacy considerations.

## **10. STATISTICAL CONSIDERATIONS**

The sections below indicate the overall structure and approach to the analysis of this study. A detailed Statistical Analysis Plan (SAP) incorporating these sections below will be prepared separately. The SAP will outline all data handling conventions, including software, and specify additional statistical methods to be used for analysis.

The study objectives are listed in [Section 1](#).

### **10.1 Study Endpoints, Subsets, and Covariates**

Efficacy and safety endpoints that will be evaluated are identified in the following sections.

The primary efficacy and safety analysis time point is at Week 25 for patients who received every 4-week dosing (Cohorts A-C) and at Week 27 for patients who received weekly or biweekly dosing (Cohorts D and E). For patients continuing treatment beyond the primary

analysis time point additional supportive efficacy and safety analyses will be repeated at the completion of Study Drug treatment.

### **10.1.1 Primary Endpoint(s)**

The primary efficacy endpoint is the percent change in Lp(a) from baseline at the primary analysis time point achieved by ISIS 681257 compared to pooled placebo.

Lp(a) levels will be analyzed from patient blood samples taken at specified time points throughout the study.

### **10.1.2 Secondary Endpoints**

The secondary endpoints include the following parameters from baseline at the primary analysis time point for ISIS 681257 compared to placebo:

- Percent change from baseline in LDL-C
- Proportion of patients who achieve plasma Lp(a)  $\leq$  50 mg/dL
- Proportion of patients who achieve plasma Lp(a)  $\leq$  30 mg/dL
- Percent change from baseline in apoB
- Percent change from baseline in OxPL-apo(a)
- Percent change from baseline in OxPL-apoB

### **10.1.3 Safety Endpoints**

The safety analysis will be performed using the following parameters:

- AEs
- Vital signs and weight
- Physical examinations
- Clinical laboratory tests (serum chemistry, hematology, coagulation, urinalysis)
- Proportion of patients with platelet drop by severity, including platelet drop below lower limit of normal (LLN), platelet drop greater than 30% from Baseline, or any platelet drop meeting stopping rules.
- Proportion of patients with liver adverse events by severity, number of patients meeting liver stopping rules, and change in liver function tests by severity.
- Proportion of patients with renal events by severity, number of patients meeting renal stopping rules, and change in renal function tests by severity.
- ECGs
- Use of concomitant medications

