### **8.6.3 Stopping Rule for Platelet Count Results**

#### Stopping Rules for Platelet Count Results

Actions to be taken in the event of a low platelet count are summarized in [Table 3](#) below.

In the event of any platelet count less than 50,000/mm^3, or a platelet count less than 75,000/mm^3 that occurs while the patient is already on reduced dose, dosing of the patient with Study Drug will be stopped permanently (Table 3). Platelet count will be monitored daily until 2 successive values show improvement then monitored every 2-3 days until platelet count is stable.

Administration of steroids is recommended for patients whose platelet count is less than 25,000/mm^3. Recovery in platelet count may be accelerated by administration of high dose

steroids. Treatment guidelines for immune thrombocytopenia (Provan et al. 2010) recommend Dexamethasone 40 mg daily for 4 days every 2-4 weeks for 1-4 cycles; Prednis(ol)one 0.5-2 mg/kg/d for 2-4 weeks then taper; or methylprednisolone 30 mg/kg/day for 7 days (**note:** may require continuation with oral steroids after methylprednisolone).

In the event of a platelet count  $< 75,000/\text{mm}^3$  and  $> 50,000/\text{mm}^3$ , and in the absence of major bleeding or clinically-relevant non-major bleeding (defined below; Schulman et al. 2005), dosing of a patient with Study Drug should be suspended temporarily until the platelet count has recovered to  $> 100,000/\text{mm}^3$ . If dosing is continued it must be at a reduced dose as shown in Table 3. The suitability of the patient for continued dosing will be determined by the Investigator in consultation with the Study Medical Monitor and will be based on factors such as the original rate of decline in the patient's platelet count, whether any bleeding events were experienced by the patient, and the speed of recovery of platelet count after interruption of dosing.

If, after reintroduction of Study Drug, the platelet count again falls below  $75,000/\text{mm}^3$ , then dosing of the patient with Study Drug will be stopped permanently.

Once a patient commences weekly monitoring this frequency of monitoring should continue irrespective of whether the platelet count rises into the normal range.

Any unreportable platelet count result must be rechecked and determined not to have met a stopping rule before dosing can continue.

Definition of Major Bleeding Events (Schulman et al. 2005):

- Fatal bleeding, and/or

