**Table 3 Actions in Patients with Low Platelet Count**

Platelet Count on Rx	Drug Dose	Monitoring
Normal range, > 140K/mm 	No action	Monitor every 2 weeks
100K-140K/mm 	No action	Closer observation Monitor every week*
75K-100K/mm 	Permanently reduce as follows: For Cohort A: reduce to 10 mg every 4 weeks For Cohort B: reduce to 20 mg every 4 weeks For Cohort C: reduce to 30 mg every 4 weeks For Cohort D: reduce to 10 mg every 2 weeks For Cohort E: reduce to 10 mg every week	Closer observation Monitor every week*
50K-75K/mm 	Pause dosing When platelet count returns to > 100K/mm  restart dosing as follows only if approved by Sponsor Medical Monitor: For Cohort A: reduce to 10 mg every 4 weeks For Cohort B: reduce to 20 mg every 4 weeks For Cohort C: reduce to 30 mg every 4 weeks For Cohort D: reduce to 10 mg every 2 week For Cohort E: reduce to 10 mg every week or Permanently discontinue Study Drug if it occurs while on already reduced dose	Closer observation Monitor every 2-3 days until 2 successive values show improvement Consider discontinuation of antiplatelet agents/non-steroidal anti-inflammatory drug (NSAIDS)/ anticoagulant medication
25K-50K/mm 	Permanently discontinue Study Drug	Closer observation: Monitor daily until 2 successive values show improvement then monitor every 2-3 days until platelet count stable Discontinue antiplatelet agents/NSAIDS/anticoagulant medication while platelet count < 50K/mm  if possible
< 25K/mm 	Permanently discontinue Study Drug	Closer observation: Monitor daily until 2 successive values show improvement then monitor every 2-3 days until platelet count stable Steroids recommended** Consider need for hospitalization and referral to hematologist Discontinue antiplatelet agents/NSAIDS/anticoagulant medication while platelet count < 50K/mm  if possible

\* Once a patient commences weekly monitoring this frequency of monitoring should continue irrespective of whether the platelet count rises into the normal range.

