#### **8.12 Safety Monitoring Compliance**

Compliance with safety monitoring requirements and treatment stopping rules must be documented by the Study Center staff.

Patients and the Study Investigators are required to adhere to a strict program of monitoring of platelet count, and liver and renal function as described in [Section 6.2.1](#), [Sections 8.5.1-8.5.3](#), and [Sections 8.6.1-8.6.3](#).

Patients will be required to have platelet counts every 2 weeks for the duration of the study and must not receive Study Drug without an interpretable platelet count result in the prior 2 weeks, in

which case the Investigator must contact the patient to hold dosing until a new platelet count is obtained and reviewed, and will document this contact.

Patients will also be required to have renal function testing and assessment of biomarkers of renal damage every 2 weeks, and must not receive Study Drug if there are no test results for parameters considered critical to patient safety available within the prior 2 weeks. In such a case, the Investigator must contact the patient to hold dosing until these or new tests are obtained and reviewed.

Adherence to the program will be closely monitored by the Sponsor, and patients and trial sites that are unable or unwilling to comply with this important risk mitigation program will be discontinued from the study.

Patients should be informed of the possibility and risks of a reduction in platelet count, and of potential hepatic and renal risks, and the importance of adherence to the monitoring program. Any case of a platelet count reduction to levels below 50,000/mm^3 (Grade 3 or Grade 4) is considered an adverse event of special interest and should be reported in an expedited fashion to the Sponsor.

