#### **9.4.3.2 Severity**

The severity of AEs and SAEs will be graded based on criteria from the Common Terminology Criteria for Adverse Events (CTCAE) Version 4.03, June 2010 (refer to [Appendix D](#)). Any AE not listed in Appendix D will be graded as follows:

- **Mild:** The event is easily tolerated by the subject and does not affect the subject's usual daily activities
- **Moderate:** The event causes the subject more discomfort and interrupts the subject's usual daily activities
- **Severe:** The event is incapacitating and causes considerable interference with the subject's usual daily activities

If the event is an SAE, then all applicable seriousness criteria must be indicated (criteria listed in [Section 9.3.3](#)).

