## Appendix A Schedule of Procedures – Weekly and Every 2 Week Dosing *Continued*

- j Blood samples to be collected after an overnight fast of at least 10 hours and preferably not more than 12 hours, unless tests are repeated for safety reasons.
- k If the platelet value, serum creatinine or liver enzyme tests are uninterpretable (e.g., due to clumping, hemolysis or quantity not sufficient) a repeat blood specimen should be re-drawn as soon as possible (ideally within 7 days). All platelet count results will be reviewed promptly (within 48 hours of receipt) by the Investigator as per [Section 6.2.1](#). Any case of a platelet count  $\leq 50,000/\text{mm}^3$  should be reported in an expedited fashion to the Sponsor.
- l Refer to [Appendix C](#) for PK Sampling schedule.
- m Women who are not surgically sterile or post-menopausal.
- n Serum and plasma samples will be collected and stored for follow-up exploration of laboratory findings and/or AEs (e.g., measurement of cytokine and/or chemokine levels, measurement of additional markers of kidney function, measurement of antibodies, etc.) in this or subsequent clinical studies of ISIS 681257.
- o Patients will continue treatment in the study until the last patient enrolled reaches 6 months of exposure, and 50% of the enrolled patients have received Study Drug for 52 weeks. When both of these milestones are met, all patients will then enter a 16-week post-treatment follow-up period.

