## **Appendix D      Grading Scale for Adverse Events Relating to Laboratory Abnormalities**

## Appendix D Grading Scale for Adverse Events Relating to Laboratory Abnormalities

The following grading recommendations for adverse events relating to lab test abnormalities are based upon the Common Terminology Criteria for Adverse Events (CTCAE) Version 4.03, June 2010.

Adverse Event	Mild	Moderate	Severe
Hematology			
aPTT prolonged	>ULN - 1.5 x ULN	>1.5 - 2.5 x ULN	>2.5 x ULN; hemorrhage
Eosinophils increased f	650 – 1,500 cell/mm 	1,501 - 5,000 cell/mm 	>5,000 cell/mm 
Fibrinogen decreased	<1.0 - 0.75 x LLN or <25% decrease from baseline	<0.75 - 0.5 x LLN or 25 - <50% decrease from baseline	<0.5 x LLN or ≥50% decrease from baseline
Hemoglobin decreased (Anemia)	Hemoglobin (Hgb) <LLN - 10.0 g/dL; <LLN - 6.2 mmol/L; <LLN - 100 g/L	Hgb <10.0 - 8.0 g/dL; <6.2 - 4.9 mmol/L; <100 - 80g/L	Hgb <8.0 g/dL; <4.9 mmol/L; <80 g/L; transfusion indicated
Hemoglobin increased	Increase in >0 - 2 g/dL above ULN or above baseline if baseline is above ULN	Increase in >2 - 4 g/dL above ULN or above baseline if baseline is above ULN	Increase in >4 g/dL above ULN or above baseline if baseline is above ULN
INR increased	>1 - 1.5 x ULN; >1 - 1.5 times above baseline if on anticoagulation	>1.5 - 2.5 x ULN; >1.5 - 2.5 times above baseline if on anticoagulation	>2.5 x ULN; >2.5 times above baseline if on anticoagulation
Lymphocyte count decreased	<LLN - 800/mm  ; <LLN - 0.8 x 10  /L	<800 - 500/mm  ; <0.8 - 0.5 x 10  /L	<500 /mm  ; <0.5 x 10  /L
Lymphocyte count increased	-	>4000/mm  - 20,000/mm 	>20,000/mm 
Neutrophil count decreased	<LLN - 1500/mm  ; <LLN - 1.5 x 10  /L	<1500 - 1000/mm  ; <1.5 - 1.0 x 10  /L	<1000/mm  ; <1.0 x 10  /L
Platelet count decreased	<LLN - 75,000/mm  ; <LLN - 75.0 x 10  /L	<75,000 - 50,000/mm  ; <75.0 - 50.0 x 10  /L	<50,000/mm  ; <50.0 x 10  /L
White blood cell decreased	<LLN - 3000/mm  ; <LLN - 3.0 x 10  /L	<3000 - 2000/mm  ; <3.0 - 2.0 x 10  /L	<2000/mm  ; <2.0 x 10  /L
Chemistry			
Acidosis	pH <normal, but ≥7.3	-	pH <7.3

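### The platelet action limits conflict at exactly 100K, 75K and 50K, and Section 10.1.3 does not name rule-driven dose reductions and pauses

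*Protocol*

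**What the plan says.** Section 10.1.3 lists as a safety endpoint "Proportion of patients with platelet drop by severity, including platelet drop below lower limit of normal (LLN), platelet drop greater than 30% from Baseline". The same item closes with a further category, worded "or any platelet drop meeting stopping rules". Section 10.1.4 makes the frequency of platelet falls one of the safety considerations for choosing a dose. The amendment table gives a statistical assessment of platelet risk as the reason for enlarging the trial to 270 patients.

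Actions on low counts appear in two places.

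- **Table 3** has five abnormal rows: 100K-140K (no dose action), 75K-100K ("Permanently reduce as follows: For Cohort A: reduce to 10 mg every 4 weeks", with a corresponding line for each other cohort), 50K-75K (pause, or permanent stop if the dose was already reduced), 25K-50K (permanent stop) and below 25K (permanent stop with added measures).
- **Section 8.6.3, text,** opens its permanent-stop rule with "In the event of any platelet count less than 50,000/mm" and extends it to counts below 75,000 on a reduced dose. Its temporary suspension applies strictly between 50,000 and 75,000. Section 8.8 repeats the stop limits.

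Section 9.3.3.1 makes counts below 50,000 an adverse event of special interest with expedited reporting. Footnote k of both Appendix A schedules starts "Any case of a platelet count" and sets the same reporting at 50,000 or less.

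On severity, Section 9.4.3.2 says "The severity of AEs and SAEs will be graded based on criteria from the Common Terminology Criteria for Adverse Events" and refers to Appendix D. There the entry "Platelet count decreased" is mild from below the LLN down to 75,000, moderate from there down to 50,000, and severe below 50,000.

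**The concern.** A patient whose count lands on a limit can be handled in two ways, each supported by the protocol. That affects patient care first. It also affects a reported result, because meeting a stopping rule is a named endpoint category: at 50,000 the classification depends on which passage is read.

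A second gap lies beside it. Section 10.1.3 moves from a fall below the LLN and a fall above 30% to the stopping rules. The two Table 3 events in between, a mandatory permanent reduction and a pause, are not named. A reduction at 75K-100K is itself an intervention that may keep the count from falling further. Counts of moderate, severe and stopping-rule events may therefore understate the platelet risk of the dose as assigned. Under Appendix D, the 75K-100K patient is graded mild together with the 100K-140K patient who needs no dose action.

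**Working it through.** **Boundary check.** Each limit was read against every passage that governs it (Protocol, Amendment 4).

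| Count | Table 3 | Section 8.6.3 text | Other passages |
|---|---|---|---|
| Exactly 100K | No-action row and reduction row | No rule for reduction at this level | Restart after a pause needs more than 100K |
| Exactly 75K, assigned dose | Reduction row and pause row | Not paused (limit is below 75,000) | Appendix D: mild |
| Exactly 75K, dose already reduced | The pause row turns into a permanent stop | Not stopped (limit is below 75,000) | 8.8: not stopped under its own platelet limit |
| Exactly 50K, assigned dose | Pause row and discontinuation row | Neither stopped (below 50,000) nor paused (above 50,000) | 9.3.3.1: not expedited; Appendix A, footnote k: expedited; Appendix D: moderate |

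The endpoint category for stopping rules is thus ambiguous at 50K, and at 75K for a patient on a reduced dose. The 100K and 75K overlaps affect who is reduced and who is paused.

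**Size for one patient.** Each active group has 45 patients, and placebo totals 45 (5 cohorts × 9). One reclassified patient changes a proportion by 1/45 = 2.2 percentage points. For comparison, Section 10.2 assumes 1.9% (placebo) and 3.8% (active) for the milder event of any count below the LLN.

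**The plan's own safety figure.** Section 10.2 states about 80% probability of at least one below-LLN patient in a group of 45 at 3.8%. The exact value is 1 − (1 − 0.038)^45 = 82.5%; the Poisson form 1 − exp(−45 × 0.038) gives 81.9%. The stated figure is acceptable as an approximation, and nothing in this point changes it.

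**What the added rows would hold.** Expected below-LLN patients are 45 × 0.038 = 1.7 per active group and 225 × 0.038 = 8.6 over all active patients. If a share s of them reached one band (assumption, since the protocol gives no split), the chance of at least one such patient is 1 − (1 − 0.038s)^n:

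- s = 10%: 16% per group (n = 45), 58% over all active patients (n = 225)
- s = 25%: 35% and 88%
- s = 50%: 58% and 99%

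**Named categories against Table 3.** The 50K-75K band corresponds to Appendix D moderate, but the pause event is not named. The 75K-100K band shares mild with 100K-140K. A further detail: the action codes in Section 9.4.3.3 offer a reduced dose only after an interruption, so a reduction without interruption has no code and must be recovered from dosing records.

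**The case against.** The stop limit is stated consistently as below 50,000 in Sections 8.6.3 and 8.8, and Table 3 is introduced as a summary of that text. Sections 6.2.1, 8.5.3, 8.12, 9.3.3.1 and 9.5.1 all put the reporting limit below 50,000, so footnote k is the outlier, and it concerns reporting rather than stopping. Exact boundary counts may be rare. All of this is fair, and it limits the likely number of patients affected.

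It does not remove the contradiction. The text itself leaves 50,000 uncovered on the assigned dose. For the 100K limit there is no text to fall back on, because the reduction rule stands only in Table 3, and Section 8.7 makes the table binding for dose adjustment. The instruction in Section 8.5 to act on the more critical of two results chooses between two measurements, not between two rules for one measurement.

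On the endpoint, it can be said that display bands belong in the SAP, that Section 10.6.2 already summarizes the amount of drug received and laboratory abnormalities by group, and that Section 10.6 lists all data. That stands for layout. It leaves the two rule-driven events without a name in the endpoint list.

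A reader might go further and infer that the severity endpoint cannot show the platelet events on which the dose will be chosen. The documents do not support this. Section 10.1.3 cites no scale, so the use of Appendix D there is an inference, and its list is open. It also names falls above 30%. Taking the LLN as 140K, as Table 3 implies, and a baseline no lower than that, a count of 90K is a fall of at least (140 − 90)/140 = 35.7%, and any count below 0.7 × 140K = 98K is captured. Nor do the documents support citing Phase 1 for harmless drift on placebo: Section 2.3.4 reports the sub-LLN fluctuations in subjects on active drug. A demand to separate counts below 25K does not follow either. Both lowest rows stop the drug permanently, and the mention of Grades 3 and 4 only glosses counts below 50,000.

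**Conclusion.** The point holds as a contradiction in the platelet action limits at 100K, 75K and 50K, and in the reporting limit at 50,000. It should be corrected because it affects patient handling and a named endpoint. The effect on results is 2.2 percentage points per affected patient in a group of 45. How many patients would be affected cannot be derived from the protocol: it gives neither the reporting precision of the counts nor their distribution. If counts are reported in whole thousands (assumption), exact values are possible ordinary results.

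Naming the reduction and pause events is a modest addition to this. It rests on the reasoning that a rule-driven reduction may prevent lower counts; the protocol gives no data on how often. No sample-size or power figure is wrong on this account.

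**What to change.** Rewrite the Table 3 rows so that they do not overlap, with one inequality at each of 100K, 75K and 50K. Carry the same inequalities into Sections 8.6.3, 8.8 and 9.3.3.1 and into footnote k of both Appendix A schedules. The sponsor decides on which side each limit falls.

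In Section 10.1.3, add the proportion of patients per arm meeting the Table 3 reduction row and the proportion meeting the pause row, each reported separately from permanent stops. State in Section 10.1.4 that both will be considered in dose selection.

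The cost is protocol wording and a few table rows. Platelet counts are collected every 14 days and dosing is entered in the eCRF (Section 8.11), so no new data are needed. The drawback is small numbers: with about 1.7 below-LLN patients expected per active group, many cells will hold zero or one patient and should be read descriptively.
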